#### 3.3 Power and sample size

The primary outcome is change in SBP between the two randomized assignments. Our power calculation is based on the 12-week means and variances from the DASH-Sodium trial, where the 12-week between-group difference in SBP was -8.9 mm Hg. With 75 people in each arm, we will have sufficient power to detect a difference in SBP of -5.8 mm Hg (type 1 error of 0.05, power of 0.85; assuming a standard deviation of 11.85 and 11.4 for control and intervention groups based on the DASH-Sodium trial). We will over-recruit up to at least 176 participants to account for a 15% attrition rate.

With respect to secondary endpoints, we will have sufficient power to detect small differences of 15% or less in the following secondary endpoints: wake-time SBP, BMI, cholesterol, triglycerides, and hemoglobin A1c. Regarding adherence, we will be able to detect changes of 13.0%–29.5% in self-reported fruit and vegetable intake, urine sodium and potassium, and 24-hour recall potassium. These differences are smaller in magnitude than the actual differences observed in prior trials.

#### 3.4 Secondary Pre-specified Subpopulations Analysis

We will repeat the primary analysis to evaluate the effect of the intervention within the following subpopulations:

- 1. Age (≥65 vs < 65 years)
- 2. Biologic sex (female or male) based on index participant
- 3. Meal preparer status of the index participant
- 4. Baseline body mass index (≥30 vs <30 kg/m²)
- 5. Baseline hemoglobin A1c (5.7 to <6.5%, <5.7%)
- 6. Family size (single family versus more than 1 participant)
- 7. Baseline SBP (following the randomization scheme)

We will fit generalized estimating equations restricted to the strata of interest. Three-way interaction product terms will be used to assess effect modification by baseline characteristic. Note these analyses are contingent on having sufficient number of participants in each strata. The strata involving baseline SBP will be performed regardless of number, following our randomization scheme.

Other stratified or subpopulation analyses based on baseline characteristics may be performed for hypothesis generation beyond the main study.

#### 3.4 Sensitivity analyses

In our primary analysis, we will include all measurements performed within the intended 3-month visit window, including those from participants with medication changes and

those with only one of the intended two sets of triplicate measurements over two visits at 3-months post-randomization. To address these situations, we have pre-specified the following sensitivity analyses.

#### Medication changes

First, in sensitivity analyses, we will exclude blood pressure observations from participants with medication changes as follows. Observations from participants with changes in medications during the 3-month active intervention period will be excluded from 3-month and 6-month comparisons. Observations from participants with changes in medications during the maintenance phase before the 6-month visit (i.e., 3 to 6 months post-randomization) will be excluded from 6-month comparisons only.

Second, we will tabulate and report the number with changes in antihypertension medication by direction of change (increase/start, decrease/stop, no change) according to intervention assignment.

Third, we will add 10 mm Hg (systolic) and 5 mm Hg (diastolic) to their follow-up visit measurement for those who started or intensified hypertension treatments. Conversely, for those with a reduction or cessation in antihypertensive medications we will subtract 10 mm Hg (systolic) and 5 mm Hg (diastolic) from the follow-up visit measurement. This approach has been adopted by others. We will also use the approach described by Law et al, i.e., adjustedsystolic = 1.11\*[systolic blood pressure] – 7.00 and adjusteddiastolic = 1.12 \*[diastolic blood pressure] – 5.81.

Fourth, we will calculate the hypertension daily dose, using the approach by Min et al to examine the effect of the intervention on treatment intensity. The hypertension daily dose is a continuous variable, but we anticipate it will require log-transformation.

#### Protocol deviations in the number of blood pressure measurements

In sensitivity analyses, we will exclude blood pressure observations from visits with protocol deviations in blood pressure measurement, specifically (1) having only 1 of the 2 intended triplicates measures or (2) measurement on an arm side (left or right) that did not match the baseline side.

#### Protocol deviations in the timing of blood pressure measurements

In sensitivity analyses, we will include those excluded from the primary analysis for having measurements outside the intended visit window (i.e., <105 days of when the intervention started for the 3-month visit and <270 days of when the intervention started for the 6-month visit).

#### Protocol deviations with respect to adherence

In other sensitivity analyses, we will also perform a per protocol analysis whereby we exclude participants, whose adherence to the grocery intervention was <85% based on dietary compliance records. This will be reported in the Supplement of the primary paper.

#### 4 Other outcomes

#### 4.1 Adherence

Compliance will be quantified by (1) 24-hour urine sodium and potassium (2) 24-hr dietary recall, estimating servings of DASH food groups as well as nutrients consumed, (3) Rapid Block screener for fruit, vegetable, fat, and sodium, 9,10 and (4) DASH Diet Index. 11 The data will be reported by treatment group.

#### 4.2 Secondary Endpoints

We will examine the effect of the DASH-patterned grocery intervention on the following additional outcomes, testing the null hypothesis that there is no difference in the following outcomes between the DASH-patterned groceries and the self-directed intervention. We will examine the distribution of all variables. We will use generalized estimating equations with a robust variance estimator and a normal family identity link for normally distributed outcomes or a binomial distribution, logit link for binary outcomes. A visit term will be used to compare changes between 3 months versus baseline, 6 months versus 3 months, and 6 months versus baseline with a product (interaction) term to compare changes across intervention. Continuous variables with non-normal residuals will be log-transformed with effects reported as a percent change. If residuals are still not normally distributed even after log transformation, we will apply non-parametric approaches.

- Seated, office-based, diastolic blood pressure: This will be based on the average of three visits at baseline (two screening visits and the randomization visit each with 3 measurements; nine measurements total), two 3-month follow-up visits (each with 3 measurements; six measurements total), and two 6-month follow-up visits (each with 3 measurements; six measurements total). This is a continuous variable that we anticipate will follow a normal distribution.
- Ambulatory blood pressure monitoring: We will determine the mean waketime systolic and diastolic blood pressure (intervention & observation phases) measured at baseline, 3-months, and 6-months after randomization. This is a

continuous variable that we anticipate will follow a normal distribution.

- Body Mass Index (BMI): This is derived from a height measurement at baseline and two weight measurements at baseline, 3-months, and 6-months. This is a continuous variable that we anticipate will follow a normal distribution.
- 24-hour urine potassium/creatinine and sodium/creatinine ratio: This is collected after a clinic void over a 24-hour period at baseline, 3-months, and 6-months. These continuous variables are often skewed and may require log-transformation in which case they will be reported as a percent change. We will examine potassium/24hr period and sodium/24hr period as well.
- Hemoglobin A1c: Measured in whole blood at baseline, 3-months, and 6-months. This is a continuous variable we anticipate will follow a normal distribution.
- Lipid concentrations: Measured in fasted serum specimens collected at baseline, 3-months, and 6-months. This includes total cholesterol, high density lipoprotein cholesterol, derived low density lipoprotein cholesterol, and triglycerides. These are continuous variables. Triglycerides typically require logtransformation. We will examine the distributions of the other lipid types prior to analysis.
- Serum potassium and creatinine: Measured in fasted serum at baseline, 3-months, and 6-months as part of a basic metabolic panel. These are continuous variables we anticipate will follow a normal distribution.
- Daily intake of fat, fruits, and vegetables: Assessed via questionnaire inperson and via phone call using a validated food screener. 9,10 This is a measure of adherence. We will focus on assessments performed at baseline, 3 months, and 6 months after randomization (12-month assessments will not be the focus of our primary analysis). We anticipate this continuous variable may have a nonnormal distribution, requiring log-transformation.
- 24-hour dietary recall: Assessed via questionnaire measured at baseline, 3-months, and 6-months after randomization. This will be used to determine a DASH Diet Index. We anticipate this will not follow a normal distribution, requiring log-transformation.

### 5 Missing data

We will employ a number of recommended strategies to prevent missing data:

- A simplified data collection schedule that minimizes participant burden;
- Intention-to-treat analysis that includes following participants according to the data collection schedule regardless of compliance with the study intervention;
- Frequent engagement with the participants through visit reminder calls or notes;
- Contiguous windows of time during which specific follow-up visits are allowed;
- Monetary incentives to encourage enrollment and continued participation;
- Rigorous training of clinic staff emphasizing the importance of
  - Positive and warm interpersonal relationships between the participants and study staff
  - Study commitment during the consent process to ensure that potential participants understand the importance of completing the study
  - Addressing participant concerns to minimize dissatisfaction
  - Collecting data even if a participant discontinues the study treatment
  - Reasons for any drop-outs will be documented.

We will perform the following sensitivity analyses using established methods for addressing missingness in clinical trials (if needed): use of out-of-window blood pressure measurements, multiple imputations at the individual level, and best and worst-case scenarios. We will compare the results from these approaches with primary analysis results to assess the primary result's robustness to the effects of missing data. Further, we will compare the baseline characteristics of complete cases and participants with missing measures between the two assignments.

## 6 Safety outcomes

We will compare self-reported symptoms that are thought to potentially arise from the diet. The symptoms will be summarized by the counts and proportions of participants in each group and overall. The treatment groups will be compared with respect to safety outcomes by using a chi-square test if there are enough events (Fisher exact test when there are expected cell counts less than 5).

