Blood work will be done at designated study visits. Common but less serious risks of phlebotomy include minor bleeding, bruising, swelling and pain at the phlebotomy site. Rare but more serious risks from phlebotomy include vasovagal syncope or infection. There is no alternative to phlebotomy for measuring serum biomarkers and all of these risks exist in the course of routine

medical care. To minimize any additional risk, the frequency of phlebotomy is kept to a minimum and will be drawn by trained staff using aseptic techniques.

Risks related to dietary changes

The diet intervention is patterned after standard recommendations for a healthy diet and should pose minimal risk for participants. Nevertheless, any dietary changes can cause some symptoms, and there may be a risk of a reaction to new food types. Common reactions include rash or hives, itching or watery eyes, wheezing or difficulty breathing, and itching and/or swelling of the mouth and throat. Participants might experience mild gastrointestinal discomfort related to a diet that has higher amounts of fiber, dairy, fresh fruits and vegetables than they usually consume. These symptoms are generally mild and resolve quickly.

Participants will be monitored for these reactions and their grocery orders can be modified as needed. Severe allergies or reactions to new foods should be rare and care will be taken to avoid any known food allergens. Should a reaction occur, we will recommend that the participant avoid the food item and seek medical care.

Risks related to family members

Participants assigned the dietitian-directed intervention will be provided a food safety handout for family members that might eat some of the groceries. This handout has information about allergies, food intolerance, and food recalls.

Risks related to food recalls or food storage issues

We will regularly monitor Amazon Fresh and Instacart for food recalls that might impact participants. We will notify participants of any recalled products within 3 business days of discovery.

Identifying patients with high BP (hypertension)

We anticipate that the intervention will decrease participant's BP. However, if we discover unusually high BP at our study visits, we will implement the following safety procedures.

- For an average SBP 160-179 mm Hg or DBP 105-109 mm Hg, we will recommend that the participant seek care with their usual provider within 1 month, and email the study clinical team

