#### 3.2 Primary analysis

Our primary comparison is the net effect of randomized assignment (dietitian-assisted vs. self-directed shopping) on office SBP from baseline to 3- (primary) and 6-months post-randomization. Office SBP will be based on the average of three visits at baseline (two screening visits and the randomization visit each with 3 measurements; nine measurements total), two 3-month follow-up visits (each with 3 measurements; six measurements total), and two 6-month follow-up visits (each with 3 measurements; six measurements total). We will first confirm that the residuals of office SBP are normally distributed (if not it will be log-transformed). Modeling will be performed using generalized estimating equation (GEE) models with a treatment-by-visit interaction term. We will perform an intent-to-treat analysis. The visit term will be used to compare changes between 3 months versus baseline, 6 months versus 3 months, and 6 months versus baseline with a product (interaction) term to compare changes across intervention. Models will be adjusted for ZIP code or baseline blood pressure in sensitivity analyses.

Our hypothesis is that 12 weeks of dietitian-assisted, home-delivered, low sodium, DASH groceries will lower office SBP compared to 12-weeks of self-directed grocery shopping. The null hypothesis is that there will be no difference in office SBP between the two intervention arms. The comparison between the two treatment groups will be performed by comparing the regression coefficient for treatment with zero (a two-sided alpha of <0.05 will be considered statistically significant for the primary comparison at 3-months.

For additional pre-specified sensitivity analyses and subgroups to assess effect medication, see below.

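### Diet symptoms are compared between arms only by a chi-square or Fisher test, so the planned analysis does not show how large an excess remains compatible with the data

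*SAP*

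**What the plan says.** SAP section 6 covers self-reported symptoms that might arise from the diet. The descriptive part is: "The symptoms will be summarized by the counts and proportions of participants in each group and overall". The comparative part is: "The treatment groups will be compared with respect to safety outcomes by using a chi-square test if there are enough events", with Fisher's exact test when an expected cell count is below 5. The section names no risk difference, risk ratio, confidence interval, significance level or visit, and it does not say how baseline symptoms are handled.

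The models that would yield effect estimates do not reach these data. The generalized estimating equations in SAP section 4.2 apply to a list of secondary endpoints that includes serum potassium and creatinine but not diet symptoms. In Protocol section 13 the models apply to effectiveness and adoption endpoints.

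The symptom questionnaire is given at baseline and at 3, 6 and 12 months (Protocol section 7). On risk, Protocol section 12 (risks related to dietary changes) says that the diet "should pose minimal risk for participants", and then adds that mild gastrointestinal symptoms may occur.

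**The concern.** A test of no difference answers only whether equality can be rejected. It does not say how large an excess the data leave open, and that is the question for tolerability. The protocol expects some symptoms from more fiber, dairy and produce, collects them at four time points, and aims to inform wider use of the program. A safety table of proportions and p-values would leave the size of any excess unstated.

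The sample size was set for systolic blood pressure: "With 75 people in each arm, we will have sufficient power to detect a difference in SBP of -5.8 mm Hg". Nothing in the documents sizes the trial for symptoms, so a moderate true excess could well end in a non-significant test.

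**Working it through.** **Inputs from the documents.** 75 analysable participants per arm; 176 recruited at 1:1, or 88 per arm, and 88 × 0.85 = 74.8 after the planned 15% attrition (SAP sections 3.1 and 3.3). The test rule comes from SAP section 6. That section gives no significance level, so two-sided 0.05 is borrowed from the rule for the primary outcome in SAP section 3.2: "a two-sided alpha of <0.05 will be considered statistically significant for the primary comparison at 3-months".

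**Assumed inputs.** Symptom rates in each arm. The documents give neither a background rate nor a relevant excess, so a range is shown.

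**Step 1: the plan's own figure.** The SAP states "type 1 error of 0.05, power of 0.85" for 5.8 mm Hg, "assuming a standard deviation of 11.85 and 11.4 for control and intervention groups".
- Combined SD = √((11.85² + 11.4²)/2) = 11.63.
- Standard error = 11.63 × √(2/75) = 1.90.
- Power = Φ(5.8/1.90 − 1.96) = 0.86, or 0.859 with the noncentral t distribution.

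The stated 0.85 is reproduced. It concerns blood pressure only.

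**Step 2: power of the planned symptom test.** Both binomial distributions were enumerated exactly. The uncorrected chi-square test was used, or Fisher's test when an expected count was below 5, and significant results in the direction of more symptoms on DASH were counted.

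| Self-directed vs DASH (assumed) | Power, 75 per arm | Power, 88 per arm |
|---|---|---|
| 5% vs 10% | 20% | 23% |
| 10% vs 20% | 41% | 46% |
| 20% vs 30% | 29% | 34% |
| 5% vs 15% | 55% | 62% |
| 10% vs 25% | 70% | 76% |
| 20% vs 40% | 77% | 84% |

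A normal approximation for 10% vs 20% confirms the order of size. The null standard error is √(2 × 0.15 × 0.85/75) = 0.0583, the standard error under the alternative is √((0.10 × 0.90 + 0.20 × 0.80)/75) = 0.0577, and the power is Φ((0.10 − 1.96 × 0.0583)/0.0577) = 0.40.

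**Step 3: what an interval would add.** Take 16/75 affected on DASH and 8/75 in the self-directed arm.
- The difference is 8/75 = 10.7 points and the pooled rate is 24/150 = 0.16.
- z = 0.1067/√(0.16 × 0.84 × 2/75) = 1.78, so p = 0.07.
- The Wilson 95% limits are 0.136 to 0.319 for 16/75, and 0.055 to 0.197 for 8/75.
- Newcombe lower limit: 0.107 − √((0.213 − 0.136)² + (0.197 − 0.107)²) = −0.012.
- Newcombe upper limit: 0.107 + √((0.319 − 0.213)² + (0.107 − 0.055)²) = +0.224.

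A doubling of the symptom is thus labelled non-significant, while the interval runs from −1.2 to +22.4 points. With equal counts, 8/75 in each arm, p is 1.0 and the interval is still −10.4 to +10.4 points.

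**The case against.** The strongest reply is that little information is lost. Counts and proportions by arm will be reported, so any reader can derive the difference and an approximate interval, as was done above. The symptoms are self-reported and expected to be mild. This stands, and it lowers the weight of the point. What remains is that the SAP does not fix the visit, the measure or the interval method, and does not make the estimate the result.

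A reader might draw stronger conclusions that the documents do not support:

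- **That the test misses most excesses that matter.** This needs a background rate and a relevant excess, and the documents give neither. In the table the test detects 5% vs 15%, 10% vs 25% and 20% vs 40% more often than not.
- **That low power is why the analysis cannot show what is ruled out.** A p-value alone cannot show that at any sample size. The gap is the missing interval, and limited power only makes it matter more.
- **That section 6 is the trial's whole safety analysis.** Serum potassium and creatinine are modelled between arms in SAP section 4.2, medication changes are tabulated by arm in the sensitivity analyses, and adverse events go to the IRB and DSMB under Protocol section 12.
- **That the plan equates non-significance with safety.** Neither document says so. A significant excess would contradict the minimal-risk expectation, and the protocol itself says that dietary changes can cause symptoms.

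**Conclusion.** The point holds for diet symptoms only. Their sole planned between-arm inference is a chi-square or Fisher test, with no effect estimate or interval, so the pre-specified comparison does not show how large an excess is still compatible with the data.

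At 75 per arm a non-significant result would be weak evidence against a moderate excess. Power is 20% to 41% for the smaller contrasts (5% vs 10%, 10% vs 20% and 20% vs 30%), 55% for 5% vs 15%, and 70% to 77% for the 15- and 20-point excesses shown (10% vs 25% and 20% vs 40%). These figures rest on assumed symptom rates and an assumed two-sided 0.05 level. The absence of a planned interval rests on neither.

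This is an improvement to consider rather than a defect that must be repaired. It affects what can be said about tolerability and leaves the blood pressure analysis untouched.

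**What to change.** In SAP section 6:

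- For each symptom, report the DASH minus self-directed risk difference with a 95% Newcombe or Miettinen-Nurminen interval at the 3-month visit, the end of the intervention, as the main result.
- Present 6 and 12 months as post-intervention description, and show baseline symptom prevalence by arm.
- Keep the chi-square or Fisher p-value as secondary.
- State that a non-significant test will not be reported as absence of excess symptoms.

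The cost is a few sentences in the SAP and an extra column in the symptom table, with no new data and no change to conduct. The downside is that the intervals will be wide and statements about tolerability will have to be more cautious.
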